5.3 Safety Analysis Set

The Safety Analysis Set for this study will be the same as FAS. This analysis set will be used for safety endpoints, study treatment administration and post-study therapy.

5.4 DLT-Evaluable Analysis Set

The DLT-Evaluable Analysis Set includes all subjects in the Safety Analysis Set who take $\geq 24/28$ ($\geq 85\%$) scheduled Cycle 1 doses of ZN-c5 (or less, if for reasons due to DLTs) and/or the cumulative dose of palbociclib was $\geq 85\%$ in Cycle 1 (or less, if for reasons due to DLTs) and underwent all treatment and safety procedures through Day 28 or experienced a DLT prior to Day 28. Determination of the MTD will be in the DLT-Evaluable Analysis Set.

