6.1.3 DEFINITION OF MTD AND RP2D

During both the Monotherapy and Combination Dose Escalation cohorts of the study, dose limiting toxicity (DLT) will be assessed during Cycle 1. A cohort will be expanded from 3 to 6 subjects if one of the initial 3 subjects demonstrates DLT. Cohort expansion or dose escalation will follow the rules outlined in Table 2. Subjects who do not receive at least 24/28 doses of ZN-c5 or at least 18/21 doses of palbociclib in Cycle 1 for reasons other than DLT will be replaced.

Table 2: Dose Escalation Rules

If DLT was observed in:	Then:
0 in 3 subjects	Proceed with enrollment in next cohort
1 of 3 subjects	Enroll 3 additional subjects in current cohort
1 of 6 subjects	Proceed with enrollment in next cohort
≥ 2 subjects in a cohort	Do not escalate; enroll 3 additional subjects in previous
	cohort or new intermediate dose level

The MTD is defined as the highest dose level with ≤ 1 DLT in a cohort of 6 subjects. The RP2D may be lower but will not be higher than the MTD. The MTD/RP2D for monotherapy treatment may be different than the MTD/RP2D for combination therapy.

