8.4.2 DEFINITION OF DOSE-LIMITING TOXICITY – COMBINATION DOSE ESCALATION

A DLT is a toxicity as defined below, excluding toxicities clearly related to disease progression or intercurrent illness, which occurs during the DLT evaluation period (Cycle 1) in each cohort:

- Hematologic:
 - o Grade 4 neutropenia
 - Febrile neutropenia (defined as neutropenia Grade ≥ 3 [ANC < 1000 cells/mm³] and a body temperature ≥ 38.5°C) requiring antibiotic or antifungal treatment
 - o Any Grade 4 thrombocytopenia (< 25,000/mm³ or <25.0 x 109/L)
- Nonhematologic:
 - o Grade ≥ 3 toxicities despite adequate treatment (e.g., nausea, vomiting, diarrhea)
- Other:
 - o Any palbociclib treatment delay of greater than 7 days to start Cycle 2

Subjects who do not receive at least 24/28 doses of ZN-c5 and/or at least 85% of palbociclib doses in Cycle 1 for reasons other than DLT will be replaced.

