9.3 POPULATIONS FOR ANALYSES

Full Analysis Set (FAS)

The FAS includes all subjects who receive ≥ 1 dose of study drug. This analysis set will be used for subject characteristics and efficacy endpoints.

Safety Analysis Set

The Safety Analysis Set for this study will be the same as FAS as this study is not randomized. This analysis set will be used for safety endpoints, study treatment administration and post-study therapy.

DLT-Evaluable Analysis Set

The DLT-Evaluable Analysis Set includes all subjects in the Safety Analysis Set who take ≥ 24/28 scheduled Cycle 1 doses of ZN-c5 and/or the cumulative dose of palbociclib was ≥ 85% in Cycle 1 (or less, if for reasons due to DLTs) and underwent all treatment and safety procedures through Day 28 or experienced a DLT prior to Day 28. Determination of the MTD will be in the DLT-Evaluable Analysis Set.

Pharmacodynamic and Pharmacokinetic Analysis Sets

The Pharmacodynamic and PK Analysis Sets consist of all subjects in the FAS who have the necessary baseline and on-study measurements to provide interpretable results for the specific parameters of interest.

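### The DLT-Evaluable set joins its ZN-c5 and palbociclib conditions with and/or, so combination subjects whom the protocol replaces as under-dosed still belong to the set used for the MTD

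*SAP*

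**What the plan says.** **The analysis set.** SAP section 5.4 starts from the Safety Analysis Set and requires a subject to take at least 24 of 28 "scheduled Cycle 1 doses of ZN-c5 (or less, if for reasons due to DLTs"). The palbociclib condition is attached by the words "and/or the cumulative dose of palbociclib was", with a threshold of 85% and again an exception for shortfalls caused by a DLT. It adds that the subject "underwent all treatment and safety procedures through Day 28 or experienced a DLT prior to Day 28". It closes with "Determination of the MTD will be in the DLT-Evaluable Analysis Set". Protocol section 9.3 has the same structure: "scheduled Cycle 1 doses of ZN-c5 and/or the cumulative dose of palbociclib was ≥ 85% in Cycle 1". Neither text splits the definition by study component.

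**The replacement rule.** Protocol section 6.1.3 covers both escalations and names "Subjects who do not receive at least 24/28 doses of ZN-c5 or at least 18/21 doses of palbociclib in Cycle 1" as the ones to be replaced, provided that a DLT was not the cause. Section 8.4.2, which applies to the combination only, names "Subjects who do not receive at least 24/28 doses of ZN-c5 and/or at least 85% of palbociclib doses in Cycle 1" and says that those who fall short "for reasons other than DLT will be replaced".

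**The decision rule.** Table 2 in section 6.1.3 acts on the number of DLTs in cohorts of 3 or 6. The MTD is the highest dose level with no more than one DLT among 6 subjects.

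**The concern.** The replacement rule removes a combination subject for a shortfall on either drug. The set, read literally, keeps a subject who is adequate on either drug. Someone with 28/28 ZN-c5 doses, 10/21 palbociclib doses and no DLT is therefore replaced and also counted as DLT-evaluable. The reverse case, with palbociclib complete and very little ZN-c5, is treated the same way.

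This is not a remote case. Protocol section 2.3.1 lists low blood counts as a known effect of palbociclib. The monotherapy DLT list (section 8.4.1) includes a treatment interruption of 4 days or more for drug-related toxicity. The combination list (section 8.4.2) has no such item and counts a palbociclib delay only when the start of Cycle 2 slips by more than 7 days. A palbociclib hold within Cycle 1 for toxicity that is not itself a DLT produces exactly this subject.

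Determining the combination MTD or RP2D is a primary objective. Two programmers could build different sets from the same sentence. The wording also sits badly with two other places: section 6.1.4 sizes the monotherapy 3+3 cohorts at 3 to 6 evaluable subjects, and section 7.2 says that withdrawn subjects who are evaluable are not replaced. If the under-dosed subject is called evaluable, those texts could be used to argue against replacing them.

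**Working it through.** **1. Thresholds.** The stated minima agree with 85%. For ZN-c5, 24/28 = 85.7% and 23/28 = 82.1%. For palbociclib, 18/21 = 85.7% and 17/21 = 81.0%. So 24 and 18 are the smallest counts that reach 85%, and the set and the replacement rule use matching cut-offs when palbociclib is counted in doses.

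**2. Overlap between the set and the replaced subjects.** Take every possible pair of Cycle 1 dose counts, with no DLT and full-strength palbociclib doses:

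- All pairs: 29 × 22 = 638.
- ZN-c5 adequate: 5 counts (24 to 28). Palbociclib adequate: 4 counts (18 to 21). Both adequate: 5 × 4 = 20.
- In the set under and/or: 5 × 22 + 4 × 29 − 20 = 206.
- Replaced for a shortfall on either drug: 638 − 20 = 618.
- Both in the set and replaced: 206 − 20 = 186.
- If both conditions are required, the overlap is 0.

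These are counts of possible patterns, not probabilities. They show how far the two rules disagree, not how often it would happen.

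**3. If the replacement is enrolled.** The adequately dosed subjects number 3 or 6 as planned. The retained subject adds no DLT, and a subject who does have a DLT is in the set under either reading. The DLT count is unchanged, and so is the Table 2 action. Only the denominator moves, for example 2/7 = 29% instead of 2/6 = 33%, or 7 subjects where the MTD definition names 6.

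**4. If the subject keeps a slot unreplaced.** Let p be the true DLT probability of an adequately dosed subject. The documents give no value, so a range is assumed. Assume also that one of the first three subjects is under-dosed and has zero DLT risk.

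- Three adequately dosed subjects: P(escalate) = (1−p)³ + 3p(1−p)⁵.
- One of the first three cannot show a DLT: P(escalate) = (1−p)² + 2p(1−p)⁴.

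At p = 1/3: 0.296 + 0.132 = 0.428, against 0.444 + 0.132 = 0.576.

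| Assumed p | All adequately dosed | One of first three cannot show a DLT |
|---|---|---|
| 0.10 | 0.906 | 0.941 |
| 0.20 | 0.709 | 0.804 |
| 0.30 | 0.494 | 0.634 |
| 1/3 | 0.428 | 0.576 |
| 0.40 | 0.309 | 0.464 |
| 0.50 | 0.172 | 0.312 |

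Zero risk is the extreme. A subject on full ZN-c5 and part of the palbociclib course would carry some risk, so for one such subject the right-hand column is an upper bound.

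**5. Palbociclib measure.** The set uses cumulative dose, while the replacement rule counts doses. A subject who takes all 21 doses at a strength below 0.85 × 125 = 106.25 mg passes the count and fails the cumulative test. The two rules can therefore disagree even if the conjunction is corrected.

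**The case against.** **The effect on escalation depends on a step that the protocol forbids.** Replacement is mandatory in sections 6.1.3 and 8.4.2, and the decision rule works on counts. A reader might infer that under-dosed subjects dilute the DLT rate, so that a dose is declared tolerable on inadequate exposure. The documents do not support that. No DLT rate is compared with a threshold, an extra DLT-free subject cannot offset a second DLT, and SAP section 6.6.3 plans DLTs as a listing only. This part of the objection stands and fixes the size of the point.

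**The SAP did not drive escalation.** Section 10.1.6 of the protocol gives dose-level review to the Safety Review Committee. The SAP is dated February 2023, after a May 2022 data cut-off set once the primary objectives were said to be met. This stands for the SAP, whose effect is on the reported MTD analysis. Protocol section 9.3 carries the same conjunction, however.

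**The conjunction may simply mean each drug as applicable.** One sentence has to cover monotherapy and combination, so that is probably the intent, but neither document says so.

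**The Day 28 clause might exclude under-dosed subjects.** If completing all treatment meant full dosing, the 85% thresholds would have no function, so the clause does not settle the matter.

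**The replacement sentence might mean short on both drugs.** Section 6.1.3 can be parsed that way, and it would then match the set. The combination-specific wording of section 8.4.2 makes a shortfall on either drug the natural reading. The alternative would make a subject with full ZN-c5 and no palbociclib evaluable for the combination dose.

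**Conclusion.** The contradiction is real and sits in both documents: the stated set for a primary endpoint admits combination subjects whom the protocol treats as inadequately exposed. When the replacement rule is followed, the consequence is an inflated evaluable N and an unclear denominator, with the DLT count and the escalation decision unchanged. The chance of escalating rises only if an under-dosed subject is treated as evaluable and holds a slot unreplaced. With one such subject among the first three, the rise is at most 0.71 to 0.80 at a true DLT rate of 0.20, 0.43 to 0.58 at 1/3, and 0.31 to 0.46 at 0.40. The rates, the single under-dosed subject and that subject's zero risk are all assumptions.

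A reader might also infer that the set determines the combination RP2D. That goes too far, because section 6.1.3 allows the RP2D to lie below the MTD. The point is worth correcting because it concerns who is counted for a primary objective, and not because a wrong dose has been shown to follow.

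**What to change.** Reconcile protocol section 9.3 and SAP section 5.4 with protocol sections 6.1.3 and 8.4.2 by defining DLT evaluability separately by component:

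- **Monotherapy escalation:** the ZN-c5 condition only.
- **Combination escalation:** both the ZN-c5 and the palbociclib conditions, unless the shortfall is due to a DLT.

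The test of the new wording is that no subject without a DLT is both replaced and counted as DLT-evaluable. Use one palbociclib measure, doses taken or cumulative dose, in all four places; the choice is the sponsor's. Record the change in SAP section 8, which does not mention this set at present.

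Changing the conjunction to a plain and would not be enough, because monotherapy subjects receive no palbociclib and would then fail the definition. The cost is a short rewrite of the definition in two places, no new data, and possibly a slightly smaller evaluable N.

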5.5 Pharmacodynamic Analysis Set

The Pharmacodynamic Analysis Set consists of all subjects in the FAS who have the necessary baseline and on-study measurements to provide interpretable results for the pharmacodynamic parameters of interest.

5.6 Pharmacokinetic Analysis Set

The Pharmacokinetic Analysis Set consists of all subjects in the FAS who have on-study measurements to provide interpretable results for the pharmacokinetic parameters of interest and who do not violate the protocol (i.e., not considered an important protocol deviation) in a way that may invalidate or bias the results.

6. STATISTICAL METHODS

6.1 General Data Handling Rules and Definitions

All data collected on case report forms will be provided in listings, except data collected only for confirmation of study entry criteria and for study administrative purposes. If any enrolled subject is found not having valid documented informed consent, that subject's data will be excluded from the report, except as necessary to document the error.

All analyses will be conducted using SAS version 9.4 or later.

Summary tables for continuous variables will include the following statistics: n (sample size), mean, standard deviation, 95% CIs on the mean (where applicable), median, minimum and maximum. Summary tables for categorical variables will include: n, proportion and 95% CIs on the proportion (where applicable). Unless otherwise indicated, 95% CIs for binary variables will be calculated using the binomial distribution (exact method) and will be 2-sided.

Endpoints will be summarized by relevant study part (escalation, expansion, Phase 2), actual dose level received (on the first day of treatment), therapy (mono or combination), analysis set and time point. As appropriate, changes from Baseline to each subsequent timepoint will be described and summarized. Similarly, as appropriate, the best/worst change from Baseline during the study will also be described and summarized.

The Baseline value will be the last (most recent) pre-treatment value. If there is a significant degree of non-normality, analyses may be performed on log-transformed data or nonparametric tests may be applied, as appropriate.

Missing data will be maintained as missing unless specified otherwise. For variables where missing data is imputed, the analysis dataset will contain one variable with the imputed value and the original variable with missing maintained as missing.

6.2 Subject Disposition

The number of subjects in each analysis set and the reasons for exclusion will be summarized for all subjects. In addition, the number of subjects who discontinued study treatment and study will also be summarized, along with the reasons for treatment and study discontinuation. Subject eligibility and enrollment details (study phase, cohort, reason subject was not enrolled, assigned dose/frequency) will be listed.

6.3 Protocol Deviations

Important protocol deviations will be summarized by category for all subjects.

6.4 Demographics and Baseline Characteristics

Demographic and Baseline characteristics will be summarized and listed in by-subject listings in the FAS (by dose level in Monotherapy Dose Escalation, by dose cohort in Monotherapy Dose Expansion, Combination Dose Escalation, and Phase 2).

The following demographics, baseline characteristics, medical history and prior cancer treatments will be summarized:

- Demographics variables include age at consent, sex at birth, childbearing potential (for females), race and ethnicity. Age group (18-64, 65-74, 75-84, ≥ 85) will be derived based on age.
- Baseline characteristics include ECOG PS, height and weight, measurable disease (Yes/No, defined as having any target lesion identified at baseline), ESR1 status at baseline (Wild Type, Mutant, Not Assessed) and subcategories (SNV, CNV, Insertion/Deletion) as well as Prior CDK4/6 inhibitor for advanced/metastatic disease (abemaciclib, palbociclib, or ribociclib, Yes/No).
- Medical history includes diagnoses or symptoms entered on the Medical History form. Verbatim descriptions of diagnoses or symptoms will be coded using the Medical Dictionary for Regulatory Activities (MedDRA version 25.0 or later).
- Cancer history includes stage at initial diagnosis, method of diagnosis, estrogen receptor status and result (%) at diagnosis, progesterone receptor status at diagnosis, HER2 status at diagnosis, HER2 evaluation method at diagnosis, histology, and the most recent tumor stage, estrogen receptor status and result (%), progesterone receptor status, HER2 status and HER2 evaluation method and sites of metastatic disease.
- Time since initial diagnosis in months will be derived, defined as: (date of first treatment – date of initial diagnosis + 1) / 30.4375. For the purposes of calculation, missing day of diagnosis will be imputed as 1; missing month of diagnosis will be imputed as January; no imputation will be made for missing year.
- Prior cancer treatments include radiotherapies entered on the prior cancer therapies form, prior cancer surgeries entered on the surgical history form and prior systemic cancer treatments (intent, regimen, start and end dates, best response, reason for discontinuation, date of relapse/progression on regimen) entered on the prior cancer therapies form.

Prior cancer treatments will be summarized as follows:

- Prior radiotherapy, occurrence (Yes/No) will be summarized categorically for each intent (adjuvant, advanced/metastatic, neoadjuvant, other).
- Prior systemic therapy occurrence (Yes/No) will be summarized categorically for each intent (adjuvant, advanced/metastatic disease, neoadjuvant, other), and number of prior systemic regimens (0, 1, 2, ≥ 3), number of prior systemic regimens for advanced/metastatic disease (0, 1, 2, ≥ 3) including the types of therapy: prior endocrine therapy, prior fulvestrant, prior chemotherapy, prior CDK4/6i, and prior PI3Ki.
- Number of prior systemic regimens for advanced/metastatic disease will be presented ordinally.
- Prior surgical procedure occurrence (Yes/No) will be summarized categorically.

6.5 Efficacy

6.5.1 Study Day and Visit Window Definitions

Study day is defined as the date of assessment – first date of treatment exposure + 1 for assessments that occur on or after the first date of treatment exposure; study day is defined as the date of assessment – first date of treatment exposure for assessments that occur prior to the first date of treatment exposure.

Tumor evaluations prior to first dose are assigned as baseline. Post dosing evaluations/responses during the treatment period will sequentially assigned based on chronology as Tumor Assessment 1, Tumor Assessment 2, etc. including any end of treatment assessments. Assessments collected during follow-up will be similarly assigned based on chronology as Follow-Up Assessment 1, Follow-Up Assessment 2, etc.

6.5.2 Tumor and Response Evaluations

Tumor and response evaluations, PFS and DOR analyses will be based on the FAS and repeated on the Tumor Response Evaluable Set.

Tumor and response evaluations, PFS and duration of response analyses will be based on the FAS and Tumor Response Evaluable Subjects population. Data will be summarized by dose level in Dose Escalation and by cohort in Dose Expansion, and listed in by-subject listings in the Tumor Response Evaluable Subjects population.

Clinical Benefit Rate (CBR) is the primary endpoint for the Monotherapy Phase 2 and Combination Phase 2 and a secondary endpoint for the Monotherapy Escalation Phase 1, Monotherapy Expansion Phase 1, and Combination Escalation Phase 1. It is defined as the proportion of subjects who have at least one confirmed response of CR or PR (only if subject has measurable disease), or SD \geq 24 weeks (or non-CR/non-PD \geq 24 weeks for subjects with non-measurable disease) prior to any evidence of progression. Subjects who develop PD, intolerable toxicity or death or who discontinue study treatment prior to the first post-Baseline assessment will be classified as non-responders.

A confirmed response of CR/PR means that a response of CR/PR is recorded at one visit and confirmed by repeat imaging at least 4 weeks later with no evidence of progression between confirmation visits.

In case of SD, measurements should have met the SD criteria for a minimum interval of 8 weeks (8 weeks minus the 7-day visit window) following the start of treatment. Similarly, for non-measurable disease, non-CR/non-PD should be maintained for a minimum interval of 8 weeks (8 weeks minus the 7-day visit window) following the start of treatment.

Best overall response (BOR) will be derived for each subject, based on evaluation of response at each tumor assessment visit per investigator assessment using Response Evaluation Criteria in Solid Tumors (RECIST) version 1.1 and reported in the following categories:

- Complete Response (CR)
- Partial Response (PR)
- Stable Disease (SD)
 - SD \geq 24 weeks in duration
 - 8 weeks < SD < 24 weeks in duration
- Non-CR/non-PD
- Progressive Disease (PD)

- Non-Responders (NR)
- Not Evaluable (NE)

Confirmation of PR and CR responses will follow the confirmation process contained in the following table where the best two consecutive time points are considered.

Earlier Best Response (not yet confirmed)	Later Best Response (confirmation)	Best Overall Response
CR	CR	CR
CR	No CR or missing	SD
PR	CR or PR	PR
PR	SD or PD or missing	SD
SD	NA – no confirmation needed	SD
PD	NA	PD

Responses recorded after initiation of anti-tumor therapy are not used (not evaluable) nor are PD responses after a missed visit [>126 days has elapsed since the last image-based response assessment (or first dose date if no prior response)] up to 24 weeks after C1D1. If the previous evaluable image-based response assessment is more than 24 weeks after C1D1, a PD response is considered to be "missed" if more than 26 weeks (182 days) has elapsed. In the case of stable disease, measurements should have met the stable disease criteria for a minimum interval of 8 weeks (8 weeks minus the 7-day visit window = 49 days) following the start of treatment.

Duration of SD for subjects with best overall response = SD is defined as the time from the day of first study treatment to the start of radiologic disease progression or death. If the subject does not have a radiological disease progression or death, the duration of SD is defined as the time from the day of first study treatment to the date of the last SD assessment. Taking scheduling of imaging into account, a 1 week window will be utilized such that the threshold for 24 weeks will be $23*7 = 161$ [response date – first dose date +1 ≥ 161].

When the investigator is in doubt as to whether progression of disease has occurred and therefore reassesses the subject at a later date, the date of the initial scan should be declared as the date of progression if the repeat scans confirm progression.

Objective Response Rate (ORR) is a secondary endpoint for all cohorts. It is defined as the percentage of subjects with measurable disease who have at least one confirmed response of CR or PR prior to any evidence of progression (as defined by RECIST v1.1). Subjects who develop PD, intolerable toxicity or death or who discontinue study treatment prior to the first post-Baseline assessment will be classified as non-responders.

Data obtained up until progression, or last evaluable assessment in the absence of progression, will be included in the assessment of ORR. However, any complete response or partial response which occurred after a further anticancer therapy was received will not be included in numerator of the ORR calculation.

The change from Baseline and percent change from Baseline will be calculated for each response assessment for the sum of target lesion measurements. The best (minimum) percent change from Baseline will be identified for each subject.

For further details regarding response criteria, refer to protocol Appendix 2 – Tumor Response Criteria.

Best overall response will be summarized categorically based on the four RECIST categories: complete response (CR), partial response (PR), stable disease (SD) and progressive disease (PD). The summary will also include a category for unevaluable (NE) subjects if applicable and one for non-responders (NR). PR and CR must be confirmed by repeat imaging at least 4 weeks later with no evidence of progression between confirmation visits.

The clinical benefit rate (CBR) and objective response rate (ORR) estimates will be presented along with the associated Clopper-Pearson 95% CIs.

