7.6 DISEASE ASSESSMENT FOLLOW-UP VISITS

Subjects without PD at the time of study drug discontinuation will continue to undergo disease evaluations every 12 weeks ± 7 days until confirmation of PD, initiation of the first subsequent cancer therapy, withdrawal of consent, death, loss to follow-up, or until the study is terminated.

Once a subject has confirmation of PD or has initiated subsequent cancer therapy, whichever occurs first, follow-up will discontinue.

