7.7 SURVIVAL FOLLOW-UP VISITS

Once disease progression is confirmed or the first subsequent new breast cancer therapy is initiated, whichever occurs first, the survival follow-up period begins. During this period, the patient or family should be contacted for survival follow-up every 12 weeks (± 14 days) until withdrawal of consent, death, loss to follow up, the end of study (Section 4.4) or the study is terminated earlier by the Sponsor. In addition, all subsequent breast cancer treatments will be recorded.

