6.5.3 Progression-Free Survival

Progression-free survival (PFS) is a secondary endpoint for all cohorts. It is defined as the time (in months) from the date of first dosing until the date of objective PD (as defined by RECIST version 1.1) or death (by any cause in the absence of progression), whichever occurs earlier: (date of first radiologic PD or death – date of first treatment + 1) / 30.4375.

Subjects who have not progressed or died at the time of analysis will be censored at the time of the latest date of assessment from their last evaluable RECIST assessment prior to receiving another anticancer therapy. If the subject has no evaluable visits or does not have Baseline data, they will be censored at Day 1 unless situation 3, as described in [Table 3](#), is encountered.

The distribution of PFS will be described in tabular format using Kaplan-Meier methodology², reporting estimated median (in months) with 95% CI, 25th and 75th percentiles (Brookmeyer and Crowley 1982, Klein and Moeschberger 1997) and KM estimated probabilities with corresponding 95% CI is (Kalbfleisch and Prentice 2002) at several time points (including 2, 4, 6, 8, 10 and 12 months).

Refer to [Table 3](#) for censoring rules for PFS.

Table 3 Censoring Rules for Progression-Free Survival

Situation	End Date	Censored
1. Documented radiological PD before initiation of non-study anti-cancer treatment (for subjects with missed tumor assessment, check #3)	Date of the first tumor assessment that determined PD	No
1a*. Clinical PD before initiation of non-study anti-cancer treatment (for subjects with missed tumor assessment, check #3)	Date of Clinical Progression	No
2. Death during the study with no prior PD and no prior initiation of non-study anti-cancer treatment (for subjects with missed tumor assessment, check #3)	Date of death	No

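### SAP 6.5.2 lets duration of SD run to death past other anticancer therapy or missed scans, in conflict with its own 161-day test, so a late death can count as clinical benefit

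*SAP*

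**What the plan says.** CBR is the primary endpoint of both Phase 2 parts and secondary in the Phase 1 parts. SD of at least 24 weeks is one way to meet it.

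For a subject whose best overall response is SD, SAP 6.5.2 says that duration "is defined as the time from the day of first study treatment to the start of radiologic disease progression or death". Only when there is neither event does it become the "time from the day of first study treatment to the date of the last SD assessment". The same paragraph then says that "a 1 week window will be utilized such that the threshold for 24 weeks will be" 23 × 7 = 161 days, and gives the test in brackets as "response date – first dose date +1" of at least 161. SD needs no confirmation and qualifies from day 49, so one scan at about week 8 is enough.

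Three exclusions in 6.5.2 deal with later therapy or missed scans:
- "Responses recorded after initiation of anti-tumor therapy are not used (not evaluable".
- PD responses after a missed visit are not used.
- CR or PR after further therapy is left out of the ORR numerator.

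None of them mentions death. For PFS, by contrast, SAP Table 3 counts a death as an event only in situation 2: "Death during the study with no prior PD and no prior initiation of non-study anti-cancer treatment". Situations 3 and 4 censor at the last adequate assessment before a gap in scans or before other therapy. SAP 6.5.4 applies the Table 3 rules to DOR.

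On data collection, Protocol 7.6 says: "Once a subject has confirmation of PD or has initiated subsequent cancer therapy, whichever occurs first, follow-up will discontinue". Under Protocol 7.7, however, "the patient or family should be contacted for survival follow-up every 12 weeks".

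**The concern.** Imaging stops when other therapy starts, but deaths are still recorded. A PD scan taken after that point could not be used anyway. For a subject who leaves with early SD and no RECIST progression, a later death can therefore be the only event that ends SD. Under the definition, all the time up to that death counts as stable disease on study treatment, including time on other drugs or time without scans.

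The outcome is perverse: a subject who dies late is a success, and the same subject alive is a failure. It also means that CBR and PFS treat one death in opposite ways. At stake is the derivation of the Phase 2 primary endpoint. A programmer must choose between the definition and the bracketed test, and the choice changes the result.

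**Working it through.** **The plan's own figures.**
- Threshold: 23 × 7 = 161 days, as stated.
- Combination Stage 1 early stopping: P(X ≤ 10 | n = 19, p = 0.50) = 0.676, against 68% stated.
- Monotherapy precision at n = 75: the Clopper-Pearson interval for 30/75 is 28.9% to 52.0%, half-width 11.6 points. For 37/75 the half-width is 11.8 points. The SAP states ±12%.

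**The rules applied to worked subjects.** Dates are assumed. First dose is day 1 and the only post-baseline scan is SD on day 57. Each subject stops for toxicity within four weeks of that scan, so no end-of-treatment scan falls due, and no RECIST PD is recorded.

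| Subject | Duration by the definition | Bracketed test, read as a scan date | PFS, Table 3 |
|---|---|---|---|
| A. Other therapy day 71, dies day 200 | 200 ≥ 161: success | 57 < 161: failure | Censored day 57 (situation 4) |
| A, but alive at cut-off | 57: failure | 57: failure | Censored day 57 |
| B. No other therapy, misses the next scan, dies day 175 | 175 ≥ 161: success | 57: failure | Event day 175 (situation 2; gap 175 − 57 = 118 days, within 126) |
| B, but alive with no further scan | 57: failure | 57: failure | Censored day 57 |

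Subject A shows the missing stop at other therapy. Subject B shows that copying Table 3 alone would not be enough, because a death inside the 126-day limit would still turn one early SD scan into SD of at least 24 weeks.

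**Direction.** A death cannot precede the last SD scan. Duration to death is therefore never shorter than duration to that scan, and any misclassification can only raise CBR.

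**Size per subject.**
- 1/75 = 1.3 points in a full Monotherapy Phase 2 dose cohort.
- 1/51 = 2.0 points in a Combination Phase 2 cohort.
- 1/19 = 5.3 points at Stage 1, where 10/19 stops and 11/19 continues.

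**Sensitivity, assumption only.** The documents give no rate. Suppose a fraction m of true non-benefit subjects is counted this way at a true CBR of 50%. Observed CBR is then 0.5 + 0.5m. For m = 2%, 5% and 10% that is 51%, 52.5% and 55%, and P(X ≤ 10 | n = 19) falls from 67.6% to 64.4%, 59.3% and 50.6%. This shows how the rule would act, not how often it does.

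**The case against.** The strongest reply is the bracketed test. It is introduced as an allowance for the timing of imaging and is keyed to a response date. A death is not a response. Read as the date of a scan, the test makes subject A a failure, which is the sensible answer. This stands: a reader might infer that the SAP plainly inflates CBR, but the text supports two results and does not say which governs. It does not remove the problem, because the explicit definition a few lines earlier names death as an end point.

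Four other stronger readings are tempting and not supported.
- **A stop for clinical progression as the example.** The CBR sentence in SAP 6.5.2 requires benefit before any sign of progression and does not tie this to RECIST. Protocol 9.4.5.2 does. That case is arguable; the toxicity case is not affected.
- **An error that grows as survival data mature.** SAP 8 sets a data cut-off of 18 May 2022. Survival status is not among the items it lists as collected afterwards, although some sites adopted the cut-off later.
- **A changed futility decision.** SAP 5.2 and 7 treat the Combination Phase 2 look as conditional on that part being run, and the death would have to be on record by the look.
- **An inflation of several points.** A case needs best response SD, no recorded RECIST PD and a death on or after day 161. End-of-treatment scans and 12-weekly disease assessments before other therapy will catch some progressions first. Any total rests on an assumed rate.

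**Conclusion.** The concern holds as an internal conflict in a primary-endpoint rule. Under the definition in SAP 6.5.2, a death on or after day 161 can turn one early SD scan into clinical benefit, even after other anticancer therapy or missed scans. Under the bracketed test read as a scan date, it cannot. No other rule in 6.5.2 settles the matter, and Table 3 governs PFS and DOR only.

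The effect is one-directional: 1.3 points per subject of 75, and 2.0 of 51 or 5.3 of 19 if Combination Phase 2 is run. The number of subjects cannot be derived from the documents, so no total bias is claimed. The demonstration covers best overall response of SD. For non-CR/non-PD the SAP sets a 24-week requirement but gives no rule for measuring duration.

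**What to change.** In SAP 6.5.2:
1. End duration of SD at the last evaluable non-PD assessment before non-study anticancer therapy or a missed-assessment gap, using the cut-offs of Table 3 situations 2 to 4.
2. State that the response date in the 161-day test is the date of an evaluable non-PD assessment. A death alone then cannot meet the test, and a subject whose SD ends in death needs such an assessment on or after day 161. The SAP should also say whether the same requirement is meant for SD that ends in radiologic PD.
3. State the same rule for non-CR/non-PD. Table 3's description of an adequate assessment lists only CR, PR, SD and PD, so non-CR/non-PD has to be named.
4. Derive CBR and BOR on this basis.

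The cost is a few sentences and a small programming change, with dates already needed for PFS and OS. Reported CBR may be slightly lower.
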